AA022331-NCT3652688

Updated 1-9-25

Study Protocol and Statistical Analyses for

Group-based Intervention for Alcohol, Drugs and Aggression Among Club Patrons AA022331

Principal Investigator:

[name]., Prevention Research Center, PIRE, Berkeley, CA

Co-Investigators:

[name]., Prevention Research Center, PIRE, Berkeley, CA

[name]., Prevention Research Center, PIRE, Berkeley, CA

[name]., Prevention Research Center, PIRE, Berkeley, CA

[name], Ph. D., Klein Buendel, Golden, CO.

Project Coordinator:

[name], B.S., Prevention Research Center, PIRE, Berkeley, CA

I Background information

Our prior research indicated that most (91.6%) of club patrons arrive in groups (Miller, et al., 2015). Considerable evidence indicates that peers can influence drinking and drug use (Dumas et al., 2014; O'Grady et al., 2011; Phua, 2011). The peer group can engage in preventive or protective behaviors for group members (Boekeloo &Griffin, 2009; Boekeloo et al., 2009) and prior research indicates a willingness for club patrons to look out for each other when in the club environment (Byrnes et al., 2016).

II. Purpose of Study

Our primary purpose was to engage groups of young adults who are planning an evening of partying at nightclubs and to determine whether the social group that arrived together would protect each other from harms related to drinking and drug use and partying. The intervention was designed to provide skills to identify early signs of alcohol/drug related problems as well as threats to personal safety from aggression. The intervention provided skills for individuals to intervene with each other to avoid unwanted outcomes like overuse of alcohol/drugs, experiences of aggression (physical/sexual). The primary outcome was to increase these protective actions within the group. Secondary outcomes included decreasing actual alcohol/drug use and experiences of aggression.

III. Study Design

a. Description of intervention

Nightlife Safety Plans (NSP) was designed to be a brief, group-based intervention, delivered to nightclub patrons as they entered the club. NSP was designed to encourage group members to look out for each while partying at the club. The underlying premise was to use social influences in positive, nonjudgmental ways to encourage more protective behaviors within the group. Four major objectives were addressed in this brief intervention: 1) to assess the level and type of risks related to over use of alcohol/drugs, aggression (physical or sexual) and safety within the group; 2) to develop an ability to recognize early indicators of problems that were likely to escalate; 3) to deliver practical, simple actions within the group that would lower the likelihood of negative outcomes when group members detected risks; 4) to encourage a group consensus to initiate safety actions within the group. A risk algorithm based upon survey questions at entrance and calculated in real time, predicted group risk levels for overuse of alcohol/drugs, aggression (physical or sexual), and unsafe exit (driving impaired). Computer tablets were programmed to show the specific level of risk that their group was in danger of experiencing that night based upon the algorithms. Examples of early indicators of risk behaviors likely to lead to unwanted outcomes were provided to aid early detection of problems. Finally, actions that could be taken to deescalate the situation were demonstrated.

The intervention was conveyed in visual pictures drawn by a graphic artist to convey the message with minimal reading required. Finally, each group was asked to discuss and form a consensus to the types of strategies that they were willing to implement if an early indicator was observed that might lead to an unwanted outcome for the group. There was total of 15 pages of interactive content programmed on the tablet and on average groups spent 5.5 minutes reviewing the content (SD=1 minute, 4 seconds).

b. Description of the Control Condition

The control condition consisted of information about fire safety at nightclubs. Examples of fires that had occurred in nightclubs were provided. Patrons were encouraged to identify exit locations in the club and to agree, a priori, meeting locations outside the club should they become separated in an emergency. A discussion after reviewing the fire safety materials was part of the control condition to mirror the group discussion of the experimental condition.

c. Selection and Exclusion of Subjects & Randomization procedures

There are two levels of randomization in this study. First, participants were randomly approached on the sidewalk. Social groups arriving at the club together were randomly approached using the portal recruitment methodology (Johnson et al., 2012; Miller et al., 2009, 2013b). The first person to cross an imaginary line on the sidewalk in front of the club was approached to recruit this person and their social group. Nightclubs with at least 200 patrons on a typical weekend night were contacted to seek permission to establish a data collection site outside the club. Clubs held different types of events on different nights, attracting different patrons, depending upon the event being featured. A total of 41 events across 7 nightclubs in the San Francisco area were selected for the data collection from June 2016 through October 2017. These events occurred on Friday and Saturday evenings when the attendance was the greatest. Patrons who were attending the club that evening and were arriving with at least one other person who agreed to participate were considered eligible. Anyone working that evening at the club was not eligible. A total of 352 groups, representing 959 patrons were included in the study. The study was able to recruit 25% of the groups that were stopped and given a description of the study and data collection procedures which included breath tests for estimates of blood alcohol levels and oral fluid samples for detecting drug use and surveys at entrance and exit. Retention for the sample was 88% at exit. Recruitment and data collection occurred outdoors with a data collection site adjacent to the entrance to the club. Participants provided informed consent, and all study procedures were approved by the Pacific Institute for Research Evaluation's Institutional Review Board.

d. Survey and Randomization Procedures

Once patrons agreed to participate in the study, each participant was given a unique number on a wrist band that allowed matching of individuals within a group and entrance/exit data. No names were collected to provide anonymity.

Computer tablets were handed to each participant to complete the entrance survey. Oral fluid samples for drug analyses and breath tests for determining blood alcohol level were collected during this time by trained research staff. Groups were randomly assigned to either experimental or control after the data for the entire group was collected at baseline. At this point, the research assistant was made aware of the random assignment to either experimental or control condition for the group. Randomization was determined by a randoms number table that determine whether the first group was experimental or control. Given that multiple groups were recruited simultaneously, the supervisor was tracking the assignments of condition and alerting the research assistants as to this assignment. The experimental condition consisted of the Nightlife Safety Plans (NSP) intervention described above. The control condition was given the Fire safety information described above. Given that both the experimental and control group conditions focused on safety in the club, we did not disclose to the participants which safety intervention was under investigation in this study. Once the group finished, they were given an incentive (\$15) and reminded that we would complete a survey when they exited the club with an additional incentive (\$25) offered. As patrons exited the club, they were surveyed again, using the same procedures established at entrance.

e. Measures

Primary Outcomes:

Number of Protective actions to keep the Group Safe: For each individual, five types of actions were assessed related to identifying a potential problem (observing overuse, physical, or sexual aggression) for a friend: There were 5 possible actions to keep their group members safe that were assessed at exit from club (checked in with friends to assess safety during evening, monitored group members alcohol consumption, encouraged pacing drinking, discouraged drug use, encouraged steps to sober up).

Protective action reported for physical aggression incident: Among those who experienced physical aggression, the prevalence of a group member taking action(s) to intervene was reported.

Protective action reported for sexual aggression incident: Among those who experienced sexual aggression, the prevalence of a group member taking action(s) to intervene was reported.

Secondary outcomes

Legally intoxicated: Breathalyzer readings were recorded and all participants who were at a reading of .08 % alcohol or higher, were considered to be legally intoxicated.

Prevalence of recreational drug use: Oral fluid samples were sent to an outside laboratory for analyses. Substances were assayed into the following seven categories (1) tetrahydrocannabinol (THC); (2) cocaine-including benzoylecgonine, cocaethylene, norcocaine; (3) amphetamine/3,4-methylenedioxy-methamphetamine(MDMA), including methamphetamine, methylenedioxyamphetamine (MDA), and methylenedioxyethylamphetamine(MDEA); (4) opiates/analgesics, including morphine, codeine, oxymorphone,6 a.m., hydrocodone, hydromorphone, and oxycodone; (5). methadone; (6). phencyclidine (PCP); and (7). ketamine. Any drug use was considered positive for drug use.

Leaving club with Friends arrived with: At exit, participants were asked if they were leaving the club with the same group of friends with whom they arrived.

Other Pre-Specified outcomes

Experienced sexual aggression: While at the club, the respondent was asked if someone touching them sexually in a way that they did not want to be touched or did something else sexual to the respondent that they did not want them to do

Experienced physical aggression: While at the club, respondent was asked if someone intentionally pushed, shoved, or punched

Experienced sexual harassment: While at the club, respondent was asked if sexually came on to them after indicating no interest

f. Sample characteristics

The average age of participants was 28 years and 43% were female. A fifth of the sample identified as Hispanic or Latino and racial characteristics were as follows: 44% white, 21% Asian, 18% unknown or not reported, 8% Black, 7% more than one race, 2% Native Hawaiian or other Pacific Islander, 1% American Indian or Alaska Native.

g. Analyses

Number of Protective actions to keep the Group Safe: These items were summed to create an index of protective actions for each individual. Then an average score was created within the group based upon the scores of each group member divided by the number of individuals in the group. This provided an overall indicator of how safe the group was because of the collective action of the members. *Protective action reported for physical aggression incident:* Among those who experienced physical aggression, the percent who reported some protective action by a member of their group was reported.

Protective action reported for sexual aggression incident: Among those who experienced sexual aggression, the percent who reported some protective action by a member of their group was reported.

Legally intoxicated: Percent who were legally intoxicated (BAC.08% or higher). Breath samples provided an estimate of the blood alcohol concentration (BAC) and the MarkV Alcovisor (PAS Systems International, Fredericksburg VA) was used to obtain the breath samples. The estimate of the BAC is presented as measured by this device. Given the short window of time (average of 1 hour 54 minutes, SD=1 hour, 3 minutes) that persons were in the club, only exit BAC is used to reflect drinking and this represents a cumulative total for the evening. Level of intoxication reported which reflects the legal standard of BAC= 0.08% or higher.

Prevalence of recreational drug use: Any use of recreational drugs present in oral fluid tests based upon lab results. Laboratory analyses were conducted using the Quantisal collection device (Immunalysis Corporation, Pomona, CA) to assess the following drug categories: (a)Tetrahydrocannabinol (THC); (b) cocaine, including benzoylecogonine, coaethylene, and norcocaine; (c) amphetamine/e, 4 methylenedioxy-methamphetamine (MDMA), methamphetamine, methylenedioxy-amphetiamen (MDA), and methylenedioxyethylamphetamine (MDEA); (d) opiates/analgesics, including morphine, codeine, oxymorphone, 6-acetylmorphine, hydrocodone, hydropmophone, and oxycodone; (3) methadone; (f) phycyclidine (PCP), and (g) ketamine. Self-report of GHB was also assessed (no lab tests were available for this drug). The prevalence of any drug use at exit from the club was created.

Physical Aggression experienced: Participants were asked at the exit survey whether anyone had intentionally pushed, shoved, or punched you while at the club during the evening.

Sexual aggression experienced: Participants were asked at the exit survey whether anyone had touched you in a sexual way that you did not want or do something else sexual to you that you didn't want them to do.

Leaving club with friends arrived with: The prevalence of the safety action to leave the club with the same friends with whom they arrived.

Females comprised 45.3% of the sample. Ethnicity/race was as follows: 44.2% White, 21.5% Asian, 7.9% African American, 1.7% Pacific Islander, 1.3% Native American, 7.1%

multiracial, 6.8% other, and 9.5% unknown. Slightly more than a fifth (21.1%) were Hispanic. The average age was 27.99 years (SD=6.35). The average group size was 3.38 persons (SD1.43).

Descriptive analyses were conducted for the overall group and for the experimental and control groups. To account for the clustering within event and group, mixed-model regressions in SPSS were used to test simple effects of the intervention on continuous background variables. Parallel models were conducted for categorical background variables using Mplus Version 7 (Muthen & Muthen, 1998-2015).For key outcomes, multilevel models via mixed-model regressions in SPSS 21 were conducted to account for nesting by event and group. Analyses used an intent-to-treat approach to examine assignment to the intervention as a predictor, controlling for background variables, history of drinking/other drug use and risk level. Listwise deletion was used for missing cases.

IV. Assessment of Efficacy-Overview

Exposure to the intervention, NSP, significantly increased the number of safety actions taken within the group to protect others in their group from the unintended consequences from behaviors and experiences in the club that evening related to alcohol use and drug use (Byrnes, Miller, et al., 2019a). The study found that group cohesion related to fewer safety strategies being used and that group cohesion was unrelated to AOD use (Byrnes, Miller, et al., 2019b). This suggests that more risk taking behavior may occur when groups are familiar and comfortable with each other, possibly lowering their sense of risks. The relatively low rates of experiencing physical and sexual aggression impacted the power of the intervention to assess protective actions related to physical or sexual incidents that occurred in the evening. Although the main focus of the intervention was on taking actions to reduce harms, there was also an impact on a secondary outcome related to alcohol use. For participants exposed to NSP, there was a significantly lower BAC at exit. Prevalence of recreational drug use was not impacted by the intervention but prior research (Miller et al., 2013b) indicates that few club patrons (<6%) convert from no drug use at entry to drug use at exit, indicating that recreational drug use has already been initiated prior to coming to the club. The intervention did not significantly alter the rates of physical or sexual aggression while at the club. However, aggression experiences are less under the control of the participants as persons outside the group can be the offender in these incidents. Thus, the group can respond and de-escalate the impact of the aggression but may not be effective at keeping aggressive incidents from happening. Finally, participants exposed to the intervention were significantly more likely to leave as a group and "stick together." Given that the intervention was focused on promoting looking after each other for the evening,

this was an important safety impact. There are anecdotal reports of individuals leaving the club with someone they just met or being assaulted while traveling home by themselves. However, data on the prevalence of this type of experience is not available from prior studies or this study.

Interpretation of the findings need to take into consideration that NSP was designed to impact the participants for the single evening at a club. It is unknown whether providing this type of brief intervention in real world settings could facilitate a more widespread adoption of these basic strategies as part of club safety behaviors adopted by patrons. It is unknown how the single exposure to the intervention might impact subsequent trips to a nightclub. It is unknown whether a single individual exposed to the intervention might practice any of the skills in other social groups in future evenings at a nightclub. The study has limitations introduced by only being conducted in one geographic location but the results are made more robust by the diversity of race/ethnicities, genders, gender identities, and ages represented in this sample.

V. Assessment of Safety (Adverse events, ethics)

There were no serious adverse events or adverse events connected to the intervention.

VI. Citations in this summary

Boekeloo, B.,& Griffin, M. (2009). Collegiates' intention and confidence to

intervene into others' drinking. *American Journal of Health Behavior*, 33, 91–100. doi:10.5993/AJHB.33.1.9

Boekeloo, B. O., Novik, M. G., Bush, E. N., & O'Grady, K. E. (2009). Impact of the "peers as family" dormitory wing-based intervention on college student alcohol use and its secondhand effects. *Journal of Drug Education*, 39, 339–359. doi:10.2190/DE.39.4.a

Byrnes, H. F., Miller, B.A., Bourdeau, B., Johnson, M. B., & Voas, R. B. (2016). Drinking group characteristics related to willingness to engage in protective behaviors with the group at nightclubs. *Psychology of Addictive Behaviors*, 30, 168–174. doi:10.1037/adb0000142

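### Section III.d describes a random draw only for the first group, gives no rule for later groups, and describes no concealment of the sequence from the supervisor who relays it

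*Combined protocol and SAP*

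**What the plan says.** The allocation procedure is in section III.d (Survey and Randomization Procedures) of the combined protocol and SAP.

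- **Timing:** "Groups were randomly assigned to either experimental or control after the data for the entire group was collected at baseline". The baseline comprises the tablet survey, oral fluid and breath test, taken on site by research staff.
- **Disclosure to assistants:** "At this point, the research assistant was made aware of the random assignment to either experimental or control condition for the group".
- **Role of chance:** "Randomization was determined by a randoms number table that determine whether the first group was experimental or control".
- **Who passes conditions on:** "Given that multiple groups were recruited simultaneously, the supervisor was tracking the assignments of condition and alerting the research assistants as to this assignment".

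The text does not give:

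- the rule for the second and later groups (alternation, blocks, a prepared list and a draw per group are all unmentioned);
- whether the first group means first of the study, of the club or of the event;
- who held the sequence;
- whether the supervisor could see the next condition or the baseline results.

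Section III.c reports 352 groups, 959 patrons, 41 events and 7 clubs. Section III.g adjusts for background variables, drinking and drug history, and risk level, and uses only the exit reading to represent drinking.

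**The concern.** A random start followed by a tracked order is quasi-random allocation: once the start is known, so is everything after it. The usual safeguard is to hide the next condition from whoever controls the order in which units are assigned. Here the person who tracks the conditions is on site, several groups are being processed together, and a group is assigned only after staff have spent time with it and breath-tested it. If that person knows the next condition and two groups are finishing, the choice of which one counts as next can depend on how sober, cooperative or close-knit each appears.

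At stake are the comparisons in section IV: the protective-action index, exit BAC and leaving together. Exit BAC is the most exposed. Section III.g treats it as a cumulative total for the evening, and entrance BAC is not among the named covariates. A difference between arms in entrance BAC would therefore pass into the exit result unless the survey-based covariates happened to absorb it.

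**Working it through.** The documents give no sample size calculation, alpha, allocation ratio or arm sizes, so there is no design figure to reproduce. Two checks are possible.

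**1. How many assignments had a draw of their own, taking III.d literally?**

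Inputs (III.c): 352 groups, 41 events, 7 clubs. Groups per event = 352/41 = 8.6. Let k be the number of first-group draws.

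- Share without a draw = (352 − k)/352.
- Share a tracker would guess correctly, if the rest alternate = (352 − k + 0.5k)/352.

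| First group of each | k | Without a draw | Correct guesses under alternation |
|---|---|---|---|
| Event | 41 | 311 (88.4%) | 94.2% |
| Club | 7 | 345 (98.0%) | 99.0% |
| Study | 1 | 351 (99.7%) | 99.9% |
| Every group drawn separately | 352 | 0 (0%) | 50% |

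The last row applies if the sentence is loosely worded and each group had its own table entry.

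**2. What could steering do? (illustration only)**

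Assumptions, none of them from the documents:

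- equal arms of 352/2 = 176 groups;
- every group paired with one other waiting group;
- a share q of pairs steered on a trait;
- correlation r between trait and outcome;
- no true effect and no covariate adjustment.

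The expected gap between the larger and smaller of two standard normal values is 2/√π = 1.128. So:

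- Difference between arms in the trait = 1.128q SD, which is 0.11 SD at q = 10% and 0.23 SD at q = 20%.
- Shift in the outcome = 1.128qr SD.
- Standard error of the group-level difference = √(2/176) = 0.1066 SD.
- With z = shift/0.1066, rejection rate = Φ(z − 1.96) + Φ(−z − 1.96).

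| q | r | Shift (SD) | z | Formula | Simulation (4,000 runs) |
|---|---|---|---|---|---|
| 10% | 0.3 | 0.034 | 0.32 | 6.2% | 6.6% |
| 10% | 0.5 | 0.056 | 0.53 | 8.3% | 8.4% |
| 20% | 0.3 | 0.068 | 0.64 | 9.7% | 10.0% |
| 20% | 0.5 | 0.113 | 1.06 | 18.5% | 18.2% |

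Two things shrink these rates.

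- If only half the groups had a waiting competitor, q = 20% acts like 10%, and the rate falls to about 7% to 8%.
- Adjusting for a covariate that correlates 0.5 with the steered trait lowers the q = 20% rates to 8.1% (r = 0.3) and 12.5% (r = 0.5). A correlation of 0.7 lowers them to 6.5% and 8.3%.

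**The case against.** The best defence is that this is a gap in reporting. Section III.d calls the assignment random twice. It has the supervisor tracking and relaying conditions, not choosing them, and it does not mention alternation. If every group had its own table entry, nothing was predictable. That possibility stands, and it is why the 88% is conditional. But calling the assignment random supplies no mechanism, and the only mechanism described covers the first group.

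The defence also points to real protections. Groups were approached by a line-crossing rule (III.c), consent and baseline came before assignment, and assistants learned the condition only after baseline. Oral fluid went to an outside laboratory, so those results could not have guided anyone on the night. These steps limit selection at enrolment. They do not blind the supervisor to the sequence, nor settle which of several groups in process is counted as next.

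A reader might go further and infer that staff chose which group received NSP, that the supervisor saw the breath readings, or that any bias must favour NSP. The documents support none of these. The first two are not stated. On direction, several items in the index are responses to drinking or drug use, so a more sober group may have less occasion for them. Section IV also reports fewer safety strategies in more cohesive groups. Steering sober or cohesive groups to NSP could thus lower its index while also lowering its exit BAC.

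**Conclusion.** The point holds in conditional form. As written, chance is stated to set only the first group's condition. The rule for the rest is missing, and no concealment from the supervisor is described. If later groups followed a fixed order, at least 88% of assignments were predictable to the supervisor, on the reading of first group that yields the most draws. If each group had its own draw, the share is zero, and one sentence in the protocol would settle it.

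It does not follow that the trial is biased. There is no evidence of steering, and the direction of any bias is uncertain. The rejection rates of about 7% to 18% rest on assumed q and r, on every group having a waiting competitor, and on no covariate adjustment; they show what is possible and do not estimate what happened. What can be said is that a reader cannot tell whether the trial was randomised or quasi-randomised, and the efficacy claims in section IV depend on the answer.

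**What to change.** **Design, for any further use of this procedure.** Let the tablet program, which already computes group risk in real time, hold a computer-generated list in permuted blocks of varying size within each event. It should reveal a group's condition only when that group's last baseline record is saved, so that the supervisor neither knows nor relays it in advance. The cost is a modest addition to existing software; tablets in use at the same event must draw on one shared list.

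**Completed data.**

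1. State the actual sequence rule, what first group refers to, who held the sequence and what that person could see.
2. If assignment was sequential from a random start, call the allocation quasi-random.
3. Report arm sizes, and entrance breath test, group size and risk level by arm. Section III.g already describes testing background variables by arm but does not name entrance breath test or group size.
4. Add a sensitivity analysis adjusting for entrance BAC and group size. This deals with measured imbalance only.

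A permutation test that re-draws only the starting conditions is optional. It applies only if the start was drawn per event, and because it takes the order of groups as fixed, it does not address steering of that order.

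The cost is some rewording, one table and one extra model. The claim may become somewhat more modest.

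### Is the lead primary outcome, a group average, left without a workable model because its row unit and denominator are not stated?

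*Combined protocol and SAP*

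**What the plan says.** Under Measures (III.e), the items behind the lead primary outcome exist only at exit: "There were 5 possible actions to keep their group members safe that were assessed at exit from club". Analyses (III.g) sums them for each person and then averages within the group, "based upon the scores of each group member divided by the number of individuals in the group". It treats the result as a property of the group: "This provided an overall indicator of how safe the group was because of the collective action of the members".

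For all key outcomes III.g gives one description: "multilevel models via mixed-model regressions in SPSS 21 were conducted to account for nesting by event and group", with adjustment described as "controlling for background variables, history of drinking/other drug use and risk level". On missing data it says only "Listwise deletion was used for missing cases". III.d makes the group the unit of assignment: "Groups were randomly assigned to either experimental or control after the data for the entire group was collected at baseline".

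III.c reports 41 events, 352 groups, 959 patrons and 88% retention at exit. III.g gives an average group size of 3.38 (SD 1.43).

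**The concern.** The outcome is defined at one level and the model is written for another. Person-level outcomes such as intoxication at exit suit nesting by event and group. A group average has no within-group variation, so a group random effect is redundant with one row per group and degenerate if the average is repeated on each member's row. The adjustment variables do not settle the row unit, because personal history belongs to the person while risk level (III.a) is predicted for the group.

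The divisor raises a second question. Scores exist only for people surveyed at exit. If all enrolled members are counted, an absent member in effect scores zero. The listwise-deletion sentence does not say whether a case is a person or a group.

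Section IV rests its main efficacy claim on this outcome. The standard error should reflect about 350 randomised groups, not about 844 people. The score should not depend on who happened to be surveyed on leaving.

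**Working it through.** **Inputs from the document.** 352 groups, 959 patrons, 41 events and 88% exit retention (III.c); average group size 3.38 (III.g). No alpha, power, effect size or intraclass correlation is stated.

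**Assumptions for the simulations.** Mean index 2.0, SD 1.4, group ICC 0.1 to 0.5, event ICC 0.03, two-sided 5% test, normal scores, no covariates, arms balanced within event, independent 12% loss unless noted, 2,000 replicates per setting.

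**1. Group size.** 959/352 = 2.72 enrolled per group, which does not reproduce 3.38 (352 × 3.38 = 1,190). The stated figure could be a person-weighted mean, m + variance/m: with a group-level SD of about 1.34, 2.72 + 1.34²/2.72 = 3.38. It could also count companions who did not enrol, since eligibility required only one other consenting person. The document does not say which, and the gap is not in itself an error.

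**2. Row unit.** Four layouts are conceivable.

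- *One row per group, event effect.* Any added group term merges with the residual. Only the sum of the two variances matters, and the arm comparison is unchanged. Simulated false positives: 4.2–4.6%.
- *Each person's index, group and event intercepts.* False positives: 4.5–4.8%.
- *Average copied to members' rows, group term omitted.* If all 959 rows are used, the standard error is too small by a factor of √2.72 = 1.65, so the true error is 2 × [1 − Φ(1.96/1.65)] = 23.5%. Simulation at 88% retention gives 23–24%. This layout contradicts "multilevel models via mixed-model regressions in SPSS 21 were conducted to account for nesting by event and group".
- *Average copied, group term kept.* The residual variance is zero, so the result depends on the algorithm. A REML fit that profiles out the scale gives 21–24%. In closed form without events, the standard-error ratio is √((349 − 2)/(844 − 2)) = 0.642, giving 2 × [1 − Φ(1.96 × 0.642)] = 20.8%. With the residual variance held at 10⁻⁶, 10⁻³ or 10⁻² (no event level, ICC 0.3, 1,500 replicates), the rates are 4.5%, 4.8% and 5.1%, and the standard error matches one row per group. SPSS was not tested.

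**3. Denominator.** 0.88 × 959 = 844 exit respondents, or 844/352 = 2.40 per group. With independent loss, 352 × (1 − 0.88^2.72) ≈ 103 groups lack at least one exit survey.

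| Handling, equal 88% retention | False positives | Power, true effect 0.3 |
|---|---|---|
| Divide by exit respondents | 4.2–4.6% | 66–80% |
| Divide by all enrolled (score × 0.89) | 4.8–5.0% | 60–73% |
| Drop partly surveyed groups (about 250 left) | 4.6–5.4% | 53–69% |

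With equal, similarly scattered loss, no choice of divisor creates a false effect. The weaker choices cost power, and that cannot account for a positive finding.

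**4. When a false difference would appear.** It needs the enrolled divisor together with loss that differs between arms. Assumed retention of 91% v 85% gives a spurious 0.10–0.11 points and 17–18% false positives; 89% v 87% gives 0.03–0.04 points and 6–7%. The respondent divisor stays at about 5–6% under the same losses.

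**The case for a change.** The strongest opposing case is that the stated model cannot be fitted literally to the outcome as defined. Something unstated was therefore done for the trial's lead claim, and readers cannot rule out the poor versions. Retention by arm is not given. Section IV reports that intervention participants more often left as a group, so losses might cluster differently by arm even at equal overall retention. If 25–50% of intervention-arm losses were whole groups and control losses were scattered, the enrolled divisor would give a spurious 0.05–0.10 points and 6–16% false positives.

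The omission stands, and so does the fact that group size has more than one reading here. The inference of harm does not. One sentence covers several outcomes, most of them person-level, so generic wording is the natural explanation. For the group average, the redundant term drops out and leaves a sound model. An average of members' scores is ordinarily taken over the members who have scores, and giving absentees zero sits badly with "Listwise deletion was used for missing cases". The clustered-loss case adds an assumed loss pattern to an unlikely divisor. Leaving the club together is also not the same as missing the survey together.

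Nor is analysing the person-level index clearly better. It changes the reading from per group to per person and gains 0–3 points of power (66–83% against 66–80%).

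**Conclusion.** No change to the plan is needed. The row unit, the divisor and the handling of partly surveyed groups are undescribed, and a competent analyst fills that gap with one row per group, an event effect and an average over exit respondents. Under the assumed means, variances and losses this holds false positives at 4–5%. The 21–24% rates require copied rows, and either omission of the stated group level or an untested software behaviour. The spurious-difference figures require the enrolled divisor plus loss that differs by arm in amount or pattern, which the document does not report. No error in the reported result is shown. The conclusion rests on the ordinary reading of III.g; the document does not confirm which version was run. A sentence on row unit and divisor, with exit retention by arm, would help readers, but it would describe the analysis rather than alter it.
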